CONCLUSION. The team has extensive experience evaluating and transporting EBPs. Our research suggests that while family-based CM is a well-validated EBP for adolescent SUD, its effects, like other adolescent SUD EBPs, are modest. Thus, this study will use an experimental mediation approach to identify mediating processes in treatment, with the ultimate aim of improving SUD treatment effectiveness. Backed by our experience conducting mediation and clinical studies, this study is poised to produce crosscutting implications for improving youth SUD treatments. Given the clear need to enhance effectiveness and durability of existing interventions, such work could have a dramatic impact on outcomes and services for youth.

DESIGN TIMELINE AND OVERVIEW

Data will be from a Ionaitudinal twoarmed parallel group design with 172 youth randomized to CM vs. CM+. In-person assessments will be at baseline, 2-, 4-, 6-, 9-, and 12-months postbaseline. Phone assessments will be at 1-, 3-, 5-, 7-, and 8months post-baseline.

STUDY SITES

The proposed study will be conducted with the OSLC outpatient clinic and Centro Latino Americano (CLA). Both are Medicaid-approved, HIPAA-compliant clinics employing Certified Alcohol and Drug Counselors (CADC) to deliver treatment services. While the two clinics serve all Lane County residents, CLA clients are predominantly Latino. As noted in the *Introduction*, adding CLA as a second site for this trial allows for oversampling of Latino youth, permitting an examination of differential mediation effects by ethnicity (see *Data Analysis*). Importantly, OSLC scientists regularly collaborate with OSLC clinic staff on intervention trials involving methods consistent with the proposed study. Similarly, OSLC scientists have a long history of collaborating with CLA on research and implementation projects. 149-150 Thus, the sites are optimal for ensuring adequate recruitment numbers, protocol fidelity, and successful completion of study procedures.

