The trial will involve 6 CADCs across the sites; 3 CADCs (2 from OSLC and 1 from CLA) will be randomly selected to deliver CM+ and the other 3 CADCs (2 from OSLC and 1 from CLA) will deliver standard family-based CM. Based on our experience with RCTs, we anticipate turnover and have planned for as-needed recruitment of new CADCs and case re-assignment to ensure cases remain within condition. To ensure high fidelity and reduce confounding variables (e.g., access, insurance), the study will pay for treatment in both conditions, and investigators will train and closely monitor CADC staff.

Adolescents presenting to OSLC and CLA for SUD treatment during Study Months 7-42 will be screened, and those meeting inclusion criteria will be offered the opportunity to participate pending available slots. Power calculations (presented subsequently) indicate an optimal sample size of 172. Given case flow at the clinics, and our desire to oversample Latino families, we anticipate achieving the required sample size in 3 years. Specifically, CLA treats 23 adolescents with SUD per year on average, and all of these will be approached to participate in

the trial. Assuming an 80% recruitment rate (see subsequent rationale for this rate), we expect to recruit 55 families from CLA across the 3 years. OSLC serves just over 100 cases/year on average, so case flow will provide more than enough families to recruit the remainder of the sample (49/year x 3 years = 117). Based on information from OSLC and CLA, the following demographic characteristics are expected for youth recruited across both clinics: average age = 15 years (range = 12-17 years); 84% White, 13% African American, 2% American Indian/Alaska Native, 1% Asian; 35% Latino (of any race); and 30% female.

PARTICIPANTS

Participants will include 172 youth and their primary parent/guardian. Inclusion criteria for the youth are: 1) age 12-17 years; 2) presence of current SUD; and 3) availability of a parent/guardian willing to participate. Exclusion criteria are: 1) actively psychotic, suicidal, or homicidal; and 2) PDD or mental retardation. To increase external validity, youth will be included regardless of co-morbid mental health or physical difficulties.

RESEARCH SCREENING, RECRUITMENT, AND RETENTION

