b-path. This model is more complex, simultaneously evaluating the mediator and outcome processes. To obtain this coefficient, the a-path is modeled along with the outcome model (c-path; testing for differences between CM+ and CM on substance use and externalizing behavior). With fewer outcome measurements, the model includes a during-treatment slope term and indicators to differentiate 9- and 12-month assessments, providing three estimates: during-treatment slope, change at 9 months, and change at 12 months. To obtain the b-path coefficient, a regression is specified with *during-treatment mediator slope* as a predictor of *outcome at 9 and 12 months*. This provides a targeted test of mediation, with during-treatment change in the mediator as a predictor of post-treatment outcomes.

Ethnicity effects. In close consultation with project consultant [name], and to address potential for differential effects across project clinics, formal moderated mediation tests can be performed.²⁰⁸⁻²⁰⁹ These tests determine whether observed mediation effects differ for Latino and non-Latino youth/parents. Sample size means that results are hypothesis-generating and thus will focus on estimation of confidence intervals. The same approach will be used to evaluate moderated mediation for ethnicity in Aims 2 and 3.

Confounding variables. Although randomization, the enhancement mediation design, and models addressing temporal sequencing increase the likelihood of valid causal inferences for mediation, a remaining assumption is that there are no unmeasured confounding variables for the mediator's effect. Cox et al.²¹⁰ recommends sensitivity analyses for confounder bias be used. First, VanderWeele's²¹¹ formulas identify youth/parents with the same value on the mediator but different values on the outcome, as well as youth/parents with the same value on the mediator across both CM and CM+ groups. Second, residuals from the models just detailed should be uncorrelated, and Mplus code from Imai et al.²¹² is used to determine whether the mediated effect differs based on unmeasured pre-treatment variables. Third, Mauro's²¹³ correlational method evaluates the sources of error variance from the mediation model, determining how large the effect of an omitted variable

would need to be to negate the mediated effect.

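### The exploratory Latino versus non-Latino mediation test is substantially confounded with clinic, and at CLA with the therapist pair; the plan should model the two moderators separately

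*Combined protocol and SAP*

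**What the plan says.** Study Sites explains why the second clinic was added: "While the two clinics serve all Lane County residents, CLA clients are predominantly Latino", and including it "allows for oversampling of Latino youth, permitting an examination of differential mediation effects by ethnicity". The same section gives the expected numbers: "we expect to recruit 55 families from CLA across the 3 years", 117 families from OSLC, and a sample that is 35% Latino overall. Three counselors (CADCs) deliver CM+, two at OSLC and one at CLA, and "the other 3 CADCs (2 from OSLC and 1 from CLA) will deliver standard family-based CM". Replacement of counselors who leave is foreseen.

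Under Randomization to Conditions, the urn factors are age, sex, baseline substance use severity and a schedule for arm balance. Clinic and ethnicity are not listed.

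Model Formulation says that preliminary models test and control for differences in outcomes across therapists and clinics. It names no clinic-by-condition or clinic-by-mediator term.

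Aim 1, Ethnicity effects, gives the reason for the test: "to address potential for differential effects across project clinics, formal moderated mediation tests can be performed". It then states the question answered: "These tests determine whether observed mediation effects differ for Latino and non-Latino youth/parents". Because of sample size, results are called hypothesis-generating and the emphasis is on confidence intervals. The same approach is carried into Aims 2 and 3.

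**The concern.** The paragraph uses a single Latino/non-Latino contrast for two questions: whether effects differ between clinics, and whether they differ by ethnicity. The design ties the two together, because the oversampled Latino youth come through one clinic. At that clinic, as planned, CM+ versus CM is also one counselor against another.

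Adjusting outcomes for clinic does not help when the clinics differ in the size of the treatment effect or of the mediated effect. Such a difference passes into the ethnicity interaction in proportion to the overlap. A confidence interval shows the precision of that estimate but not its bias, so caution based on sample size does not cover the problem. What is at stake is a published lead about how treatment works in Latino families that in fact reflects a clinic or a pair of therapists. It would affect all three aims.

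**Working it through.** **Inputs.** From Study Sites: CLA 23 cases a year, 3 years, 80% recruitment; OSLC 117; total 172; 35% Latino; one CLA and two OSLC counselors per arm. From Statistical Power: 155 after attrition. Assumed: CLA's Latino share *s*, therapist ICC of 0.05 or 0.10, and a clinic difference in treatment effect of 0.5 SD.

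**The plan's figures.** 23 × 3 × 0.80 = 55.2, which reproduces 55, and 55 + 117 = 172. (The printed product for OSLC, 49 × 3, is 147 rather than 117; 49 × 3 × 0.80 = 117.6. I use 117 because it gives the stated total.) Latino youth: 0.35 × 172 = 60.2, taken as 60, leaving 112 non-Latino.

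**Overlap.** Latino youth at CLA = 55*s*; Latino youth at OSLC = 60 − 55*s*; non-Latino youth at CLA = 55(1 − *s*). The correlation is

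φ = (172 × 55*s* − 60 × 55) / √(60 × 112 × 55 × 117), with denominator 6,576.

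At *s* = 0.80: (7,568 − 3,300) / 6,576 = .65. The variance inflation factor is VIF = 1/(1 − φ²).

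| Assumed CLA Latino share | Latino at CLA | Latino at OSLC | Non-Latino at CLA | φ | VIF |
|---|---|---|---|---|---|
| 51% | 28 | 32 | 27 | .23 | 1.06 |
| 60% | 33 | 27 | 22 | .36 | 1.15 |
| 80% | 44 | 16 | 11 | .65 | 1.73 |
| 90% | 49.5 | 10.5 | 5.5 | .79 | 2.69 |
| 100% | 55 | 5 | 0 | .94 | 8.16 |

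**Leakage of a clinic difference.** Suppose ethnicity has no effect and the treatment effect differs by 0.5 SD between clinics. With only a clinic main effect in the model, the spurious ethnicity-by-condition difference is about 0.5 × (share of Latino youth at CLA − share of non-Latino youth at CLA). At 60%: 0.5 × (33/60 − 22/112) = 0.18 SD. At 80%: 0.5 × (44/60 − 11/112) = 0.32 SD. A simulation (4,000 replications, n = 155, six therapists laid out as planned, least squares on one continuous outcome of the a-path type) gave 0.17, 0.32, 0.40 and 0.47 SD at 60%, 80%, 90% and 100%.

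**Leakage of therapist differences.** The same simulation, with no ethnicity effect and no systematic clinic effect, gave these rejection rates for ethnicity-by-condition at a nominal 5%:

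| CLA share | ICC 0.05, clinic main effect only | ICC 0.10, clinic main effect only | ICC 0.05, clinic × condition added | ICC 0.10, clinic × condition added |
|---|---|---|---|---|
| 60% | 7.2% | 9.0% | 5.5% | 5.0% |
| 80% | 11.8% | 19.1% | 5.0% | 5.5% |
| 90% | 14.9% | 25.4% | 5.0% | 4.9% |
| 100% | 20.0% | 29.6% | 6.4% | 6.7% |

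**Price of the adjustment.** Without therapist variance, the standard error of the ethnicity interaction is about 0.34 SD in the clinic-main-effect model. With clinic × condition added it is 0.37, 0.45, 0.58 and 1.00 SD at 60%, 80%, 90% and 100%. As a check, 0.34 × √VIF gives 0.36, 0.45, 0.56 and 0.97.

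The simulation covers the treatment-to-mediator step only, not the full parallel-process model. It also assumes that, within OSLC, ethnicity does not decide which counselor a family gets; the plan gives no rule for this.

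**The case against.** The strongest reply is that the size of the overlap is unknown. The plan gives no percentage for CLA, and at 60% there would be about 27 Latino youth at OSLC and 22 non-Latino youth at CLA, enough for partial separation at little cost. A reader might infer that the ethnicity test is nearly the same contrast as clinic. The documents do not support that; it holds only if CLA is about 90% Latino or more. The low end does sit awkwardly with the reason for adding CLA, since at 51% OSLC itself would be about 27% Latino (32/117), but that is inference.

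The reply is also right that the analysis is optional and exploratory, and that the plan commits to no conclusion about ethnicity. It asks a descriptive question about a characteristic that is not randomized. Therapists are randomized to arm and balanced as far as six allow, share core training, and are monitored for fidelity. Turnover may bring in more counselors. These measures reduce therapist differences but do not remove the confounding at CLA.

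A reader might further infer that OSLC's use of the parent-training (PMTO) teaching system makes the clinics differ. The fidelity and feasibility text shows the system in use in OSLC programs. It does not show that the trial counselors had used it or that CLA lacked it. This is at most a possible mechanism, and the point does not depend on it.

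What remains is that no planned term handles a clinic or therapist difference in the treatment or mediation paths. The stated caveat concerns sample size only. Bias appears even at a 60% share.

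**Conclusion.** The point holds as one of substantial confounding, not of near-identity. On the plan's own margins the clinic-ethnicity correlation is about .36 to .94 for CLA Latino shares of 60% to 100%, and .23 at the lowest reading of 51%. Under the assumed 0.5 SD clinic difference, between a third and nearly all of it would be read as an ethnicity difference (0.17/0.5 = 34%; 0.47/0.5 = 94%). Under assumed therapist ICCs of 0.05 to 0.10, the false-positive rate runs from 7% to 30%. These sizes rest on the assumed share, ICC and clinic difference, and on a model simpler than the planned one. The direction of the problem does not.

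It would go too far to say that the test can support nothing about ethnicity, or that the moderator should simply be renamed as clinic. If CLA were 60% Latino, that label would itself be wrong. For an exploratory analysis that is a stated reason for the second site, this is an inexpensive improvement that should be made.

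**What to change.** In Aim 1, Ethnicity effects, and by reference in Aims 2 and 3:

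- Treat clinic and ethnicity as two separate moderators, and stop presenting the ethnicity test as the answer to clinic differences.
- Report the observed ethnicity-by-clinic table.
- Report the ethnicity moderation twice, with confidence intervals: as planned, and with condition-by-clinic and mediator-by-clinic terms added.
- Where numbers allow, add the Latino versus non-Latino estimate within OSLC. At CLA shares of 80% to 100% it would rest on about 16 down to 5 Latino youth over both arms, so it may be too thin to report.
- State that confounding with clinic and therapist, as well as sample size, limits any attribution to ethnicity. The added terms do not separate clinic from the counselor pair at CLA.

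Amend the sentence on the second site's purpose in Study Sites to match.

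No new data are needed, only SAP wording and a few model terms. The adjusted ethnicity contrast will have a wider interval, slightly so if CLA is about 60% Latino (standard error 0.34 to 0.37 SD) and greatly so at 90% or more (0.58 to 1.00 SD), and the ethnicity claim will be weaker.

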EXPERIMENTAL MEDIATION AND CAUSAL INFERENCE. The experimental mediation design emphasizes evidence supporting causal inferences, and there are important conceptual and statistical considerations. As reviewed by [name], ¹⁹⁹ by randomizing youth/parents, the effect of CM+ on parent management is a causal estimate. However, the effect of parent management on drug use and externalizing behavior is not straightforwardly causal, it is potentially influenced by unmeasured confounding variables. Following [name]'s

recommendations, and to support causal inferences, this is addressed in 3 ways. First, the enhancement design directly targets the mediator—increasing probability of a causal effect between mediator and outcome. Second, longitudinal measurements of the mediator and outcomes address temporal sequencing—demonstrating that mediator effects occur before outcome effects. Third, supplemental models evaluate confounding variables—providing evidence that mediator effects are not due to confounders.

MODEL FORMULATION. The underlying model is a mixed-effects latent growth curve model with repeated measurements (level-1) nested within youth/parents (level-2), implemented in Mplus (v7.31;¹⁹⁷). As reviewed by [name],²⁰⁰ there are several options for modeling longitudinal mediation. Flexibility of growth models for targeting phase-specific change²⁰¹ are leveraged and combined with parallel process models for mediation.²⁰² In a single model, there are separate change estimates for during- and post-treatment phases, directly addressing temporal sequencing of mediators and outcomes. The UDS outcome is modeled using a Bernoulli distribution, and remaining ultimate outcomes, direct targets, and indirect targets are modeled with normal distributions. Time terms are computed using assessment dates.²⁰³ Treatment condition is a youth/parent-level predictor (level-2; CM = 0, CM+ = 1), and cross-level interactions are specified between condition and level-1 growth and phase terms. Models, as indicated, control for age, sex, race, ethnicity, SES, and treatment history. Likewise, preliminary models test, and control, for differences in outcomes across therapists and clinics. Follow-up models determine whether individual paths and mediated effects differ for males and females.

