AIM 2: DETERMINE WHETHER PARENT MANAGEMENT SKILLS (DIRECT TARGET) MEDIATE THE EFFECT OF TREATMENT ON YOUTH BEHAVIORAL REGULATION & DEVIANT PEER RELATIONS (INDIRECT TARGETS). In the parallel process model for Aim 2, the *a-path* is identical to that for Aim 1. The "outcome" model is nearly identical, the only difference being that the "outcomes" are indirect targets of treatment, behavioral regulation and peer relations. The b-path coefficient represents the association between the during-treatment slope for parent management and the 9- and 12-months post-treatment levels of behavioral regulation and peer relations.

AIM 3: DETERMINE WHETHER BEHAVIORAL REGULATION & DEVIANT PEER RELATIONS (INDIRECT TARGETS) MEDIATE THE EFFECT OF PARENT MANAGEMENT SKILLS (DIRECT TARGET) ON YOUTH SUBSTANCE USE & BEHAVIOR PROBLEMS (ULTIMATE OUTCOMES). Aim 3 uses the same approach, with one key difference: rather than treatment condition, the initial variable is parent management (the direct target of treatment) and, as such, there are repeated measurements. The *a-path* represents the effect of parent management on behavioral regulation and deviant peer relations. With both measured longitudinally, this takes the form of the during-treatment slope for parent management predicting the during-treatment slope for behavioral regulation and deviant peer relations. Although this could confound timing and sequencing of a-path effects, the results of Aim 2 will have established the extent to which there is evidence supporting a causal association between the direct and indirect targets of treatment. The outcome model is identical to that for Aim 1. The *b-path*, holding constant the effect of parent management, is the effect of the during-treatment slopes for behavioral regulation and peer relations on the post-treatment levels of substance use and behavior problems.

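### Aim 3 starts from a variable that is not randomized, but the plan states no assumption or sensitivity analysis for unmeasured confounding of its a-path

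*Combined protocol and SAP*

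**What the plan says.** The section on experimental mediation and causal inference treats the effect of CM+ on parent management as causal because families are randomized. Of the effect of parent management on the outcomes it says that "it is potentially influenced by unmeasured confounding variables".

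The Aim 1 paragraph on confounding variables follows from this: "a remaining assumption is that there are no unmeasured confounding variables for the" mediator's effect. It lists three sensitivity analyses:

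1. bias formulas, which compare mediator values with the outcome and across CM and CM+;
2. a residual-correlation analysis of whether the mediated effect depends on unmeasured pre-treatment variables;
3. a correlational omitted-variable method applied to the mediation model.

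Aim 3 is said to use the same approach with one difference: "rather than treatment condition, the initial variable is parent management". Its a-path is the "during-treatment slope for parent management predicting the during-treatment slope for behavioral regulation and deviant peer relations". The plan concedes one weakness, "Although this could confound timing and sequencing of a-path effects", and answers it by saying that "the results of Aim 2 will have established the extent to which there is evidence supporting a causal association" between direct and indirect targets. In Aim 2 that link is the b-path, described as the "association between the during-treatment slope for parent management and the 9- and 12-months post-treatment levels" of the indirect targets.

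**The concern.** With a randomized initial variable, product-of-coefficients mediation needs a no-unmeasured-confounding assumption for the mediator-to-outcome relation only, because randomization covers the rest. That is the situation in Aims 1 and 2. When the initial variable is observed, its relation to the mediator (and to the outcome) needs the same assumption. Aim 3 changes the initial variable but not the stated assumption.

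The weakness that the plan admits is one of time order. A common cause is a different problem: something that moves parenting and peers together during treatment gives a non-zero a-path even if parenting does nothing to peers. Multiplied by a real b-path, it is reported as mediation. The listed covariates (age, sex, race, ethnicity, SES, treatment history) handle measured background only. A shared influence is plausible from the plan itself, since youth report contributes both to the parent management measures and to the peer scales.

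Aim 3 is one of three specific aims and is worded in terms of the effect of parent management, so its causal reading is at stake.

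**Working it through.** **1. Which path is protected by what**

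| Aim | Initial variable | a-path | b-path |
|---|---|---|---|
| 1 | condition (randomized) | condition to parenting: randomized | parenting to outcomes: observational |
| 2 | condition (randomized) | condition to parenting: randomized | parenting to indirect targets: observational |
| 3 | parenting (observed) | parenting slope to indirect-target slope: **observational** | indirect targets to outcomes: observational |

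The Aim 2 result cited in support of the Aim 3 a-path is the Aim 2 b-path. It places parenting change before the 9- and 12-month levels, which helps with time order. It does not remove a common cause, for the reason the plan itself gives for parenting effects. The plan extends the ethnicity analysis explicitly to Aims 2 and 3; no such sentence extends the confounder analyses.

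**2. Reproducing the plan's figures**

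Inputs from the power section: R² = .07 per path, so r = √.07 = .265; N = 155 after 10% attrition (172 × .90 = 154.8); two-sided 5% from the 95% interval.

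- a-path power: Φ(atanh(.265) × √152 − 1.96) = .916. The plan states above .90, which is reproduced.
- A single-mediator simulation (2,000 to 4,000 replications) gives b-path power of .89 to .90 (stated .85). Mediated-effect power is .81 to .83 with the asymmetric interval and .67 to .68 with the Sobel standard error (stated .83, Sobel). The growth-model parameters behind the plan's simulation are not given, so I call neither difference an error.

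**3. A confounded a-path with no true effect**

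Same model, true a = 0, b = .265. An unmeasured factor U loads λ on the initial variable and on the mediator and does not act on the outcome. The spurious a-path is then λ × λ. The documents give no value for λ, so the range is assumed.

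| λ | Spurious a-path (λ²) | Mediated effect declared |
|---|---|---|
| 0 | 0 | about 4% |
| .2 | .04 | about 7% |
| .3 | .09 | about 17% |
| .4 | .16 | about 46% |
| .5 | .25 | about 78% |

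Repeat runs differ by about one percentage point. Adjusting for U brings the rate to 3–5% throughout. If U also acts on the outcome, the rate is roughly 19% to 89% for slope loadings of .3 to .5.

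**4. What a mediator-outcome check shows in this case**

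At λ = √.265 = .51 the spurious a-path equals the planned effect. The mediator-outcome residual correlation needed to bring the mediated effect to zero is .256, and it is also .256 under genuine mediation. That quantity cannot separate the two.

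**5. What the same method shows on the a-path**

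For an estimated a of .265 with standard error √(.93/153) = .078, held fixed as an approximation:

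- lower limit to zero: λ² = .265 − 1.96 × .078 = .112, so λ is about .33;
- estimate to zero: λ² = .265, so λ is about .51.

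These are the figures a reader of Aim 3 would need.

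**6. The randomized contrast as a cross-check**

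If CM+ acted on the indirect targets only through parenting at the planned path sizes, its effect on their slopes would be r = .265 × .265 = .07. Power is Φ(atanh(.07) × √152 − 1.96) = Φ(.86 − 1.96), about 14%. A null result would be expected whether or not the a-path is real.

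**The case against.** A reader might infer that the plan's checks look only at the b-path, so that a mediated effect created by a confounded a-path would pass all of them. The documents do not support that. The second analysis is worded on the mediated effect and the third on an omitted variable in the mediation model; nothing limits the third to the b-path. A confounder that also acts on the outcome leaves a mediator-outcome residual correlation (about .12 with loadings of .5 on both slopes and .3 on the outcome), which is what the second analysis concerns. The result in step 4 applies to a check confined to the mediator-outcome relation, which is an assumption about how the plan would be carried out.

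Aim 2 also counts for something. It examines nearly the same relation with better time order, and if the confounder analyses were run there they would bear on the Aim 3 a-path. The plan's sentence is hedged, referring to the extent of the evidence, and the switch of initial variable is disclosed.

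Finally, the simulation omits condition, covariates and growth structure, its loadings have no source in the documents, and at .2 the inflation is small.

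All of this stands, and it limits the point. It does not supply the missing piece: no sentence states the extra assumption that Aim 3 needs or directs any of the three analyses to its a-path. The first analysis compares CM with CM+, which is not Aim 3's initial variable, and the second is worded on pre-treatment variables, not on influences that change during treatment.

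**Conclusion.** The concern holds in this form: the assumption set stated in the plan is sufficient for a randomized initial variable and insufficient for Aim 3, and the reference to Aim 2 addresses timing only. Followed as written, Aim 3 could report a common cause of two slopes as mediation.

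The size depends on confounder strength, which is unknown. The rates in step 3 illustrate sensitivity under a single-mediator model with equal loadings; they do not estimate this trial's false-positive rate, nor do they show that the planned checks would fail. The randomized comparisons in Aims 1 and 2 are not affected. The change should be made, because it alters what Aim 3 can conclude.

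**What to change.** In the Aim 3 section:

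- State the added assumption of no unmeasured common cause of the parenting slope and the indirect-target slopes, and say whether condition stays in that model.
- Apply the correlational omitted-variable method, already planned under Aim 1, to the Aim 3 a-path as well as the b-path. Report for each the confounder strength that would bring it to zero.
- Reword the sentence that relies on Aim 2: Aim 2 bears on timing, both Aim 3 paths are observational, and Aim 3 mediation is associational.
- Optionally, show the randomized CM+ versus CM effect on the indirect targets' during-treatment slopes beside the Aim 3 result. Label it as a descriptive check with about 14% power under full mediation at the planned path sizes, neither confirming nor refuting the a-path.

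The cost is a few extra calculations on models already planned and a softer Aim 3 conclusion. No new data or design change is needed.
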